9.6 DATA MANAGEMENT

Data are gathered using EDC.

9.7 DATA ANALYSIS

This is a non-interventional, observational study to collect new real-world data (i.e., data under routine medical practice) on safety and effectiveness of Spiriva Respimat treatment in patients. Analyses are descriptive in nature. Due to the nature of the observational study, no confirmatory statistical testing is foreseen in this study.

Per local regulation, any patient who meets one of the following criteria is treated as ineligible for all analyses:

- No safety observation was documented after registration
- No required registration procedure was followed
- No valid site contract was available

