4. ABSTRACT

Name of company: Boehringer Ingelheim			
Name of finished medicinal product: SPIRIVA Respimat			
Name of active ingredient: Tiotropium bromide			
Protocol date: 15 April 2015	Study number: 205.525	Version/Revision: Ver 1.0	Version/Revision date: n.a.
Title of study:	Specific Use-Result Surveillance of Spiriva Respimat in asthmatics (patients with severe persistent asthma)		
Rationale and background:	The safety of Spiriva® 2.5 µg Respimat® 60 puffs (hereinafter referred to as Spiriva® Respimat®) in patients with severe persistent asthma under the real-world use was not confirmed in clinical trials.		
Research question and objectives:	This PMS is designed; To investigate the safety and effectiveness of Spiriva Respimat in patients with severe persistent asthma under real-world use.		
Study design:	Non-interventional, observational study based on new data collection		
Population:	Inclusion criteria: 
• Patients diagnosed with severe persistent bronchial asthma• Patient aged ≥ 15 years old• Patients who are naive to Spiriva respimat and receive Spiriva Respimat for the first time for the treatment of bronchial asthma on top of at least ICS treatment.		
Variables:	Demographics Medical history/baseline conditions Previous/concomitant therapies Pulmonary function test (peak expiratory flow rate, forced expiratory volume in 1 second, forced vital capacity), if available Asthma severity and asthma control status, if available ACQ 6 score, if available Spiriva Respimat administration Adverse event Safety laboratory test (if corresponding AEs are reported)		
Data sources:	Patients data will be gathered by electronic Case Report Form on EDC		
Study size:	300 (safety set)		
Data analysis:	Descriptive		
Milestones:	Final report will be made by 1 Apr 2018 Study result in re-examination will be submitted to PMDA (Jan. 2019)		

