9.2.2 Selection of population

9.2.2.1 Inclusion/Exclusion criteria:

Inclusion criteria:

- Patients diagnosed with severe persistent bronchial asthmaPatient aged ≥ 15 years
- Patients who are naive to Spiriva Respimat and receive Spiriva Respimat for the first time for treatment of bronchial asthma on top of at least ICS treatment.

*:Asthma severity is defined by “Table 6 Classification of asthma severity based on the present treatment (adult)” of “Japanese Guideline for Adult Asthma 2014”[P14-15105]. Most severe persistent asthma is included in “Severe persistent asthma” indication in J-PI of Spiriva Respimat.

Exclusion criteria:

- Patients who have a contraindication to Spiriva Respimat defined in the package insert for Spiriva Respimat
- Patients who have been enrolled this study before.

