9.2.2.2 Patient registration method

The registration method will be a continuous investigation system. Patients who begin treatment with Spiriva Respimat after the conclusion of the contract will be registered by entering necessary information in the EDC within 14 days whenever possible from the day of treatment initiation (inclusive).

The necessary variable for registration is gender, date of birth, start date of administration and the reason for use. And ICS treatment as of inclusion criteria will be checked in the EDC system.

Patient registration will be stopped when the target number of the study is reached. After the end of the registration period, investigators will use a signed form to confirm that patients will be registration continuously at the site. A log of all patients included into the study will be maintained at the site.

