### **5.4 OTHER VARIABLES**

#### **Demographic data and baseline characteristics:**

- Sex: male, female
- Age [years]  
Age [years] = Actual age based on the first administration of Spriva Respimat  
[REDACTED]
- Height [cm]
- Weight [kg]  
[REDACTED]
- Body mass index (BMI) [ $\text{kg}/\text{m}^2$ ]  
BMI [ $\text{kg}/\text{m}^2$ ] = weight [kg] / (height [m])  
[REDACTED]
- [REDACTED]
- Smoking status: Never smoked, Ex-smoker, Current smoker, Unknown
- Pack-Years  
[REDACTED]
- [REDACTED]
- Indication for use: Bronchial asthma, Other
- Asthma Severity: Severe persistent, Moderate persistent, Mild persistent, Intermittent, Unknown

- Duration of asthma [years]  
Duration of asthma = [First administration of Spiriva Respimat – Date of indication of asthma + 1 (if negative value, then 1)] / 365.25: Day of indication is 1.  
[REDACTED]

- Number of hospital admission due to asthma in the past year (Statistics and frequency)
- Number of urgent visit to physician due to asthma in the past year (Statistics and frequency)
- Medical history: Yes, No, Unknown  
[REDACTED]

- Concomitant diagnosis: Yes, No, Unknown  
[REDACTED]

- Previous Medication: Yes, No, Unknown  
Note: Previous medications are existing drugs, drugs which administered before initiation of the new anti-asthmatic drug, drugs of unknown starting date.  
[REDACTED]

- Concomitant Medication during treatment of Spiriva Respimat: Yes, No, Unknown
  - Note: Treated during treatment period of Spiriva Respimat regardless of the start and end date of the medication (except for the case that the end date of the medication and the start date of Spiriva Respimat are the same)SABA: Yes, No, Unknown

- Concomitant therapy: Yes, No, Unknown
- Pulmonary Function Test

- Asthma control status at baseline (see the CTP Section 9.1.1.4): Well-controlled, Insufficiently-controlled, Poorly-controlled, Unknown

- Asthma symptoms (in the daytime or at night): Yes, No, Unknown
- Use of reliever: Yes, No
- Limitation of activities, including exercise: Yes, No, Unknown
- PEFR (mean of the 7 days before each visit) [L/min]
- Pregnancy test: Yes, No, Unknown
- ACQ 6 score at baseline (each score and mean of 6 questions)
- Contraindication to Spiriva Respimat: Yes, No

[REDACTED]

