## 6.3 PATIENT SETS ANALYSED

[figure not shown]
The following two analysis sets are defined as in CTP Section 9.7. The safety set will be the basis of all demographic, baseline and safety analyses. Efficacy analysis will be on basis of the efficacy set.

- Safety set:  
This patient set includes all patients who were documented to have taken at least one dose of Spiriva Respimat except for patients who had no observation documented after entry, made invalid registration or were not under the appropriate site contact.

- **Efficacy set:**

This patient set is a subset of the safety set that includes all patients in the safety set who have baseline and at least one available on-treatment asthma control status, PEFR, FEV1, FVC or ACQ 6 score.

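### The visible analysis-set rules do not exclude on severity, indication, age or contraindication, so the efficacy result and the overall ADR frequency can include patients outside the severe-asthma objective

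*Protocol*

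**What the plan says.** **Target population.** Protocol 8 states one objective: safety and effectiveness in severe persistent asthma under real-world use. The entry criteria (Protocol 4 and 9.2.2.1) are "Patients diagnosed with severe persistent bronchial asthma", "Patient aged ≥ 15 years", and first use of the product, "for the first time for treatment of bronchial asthma on top of at least ICS treatment". The exclusion criteria include "Patients who have a contraindication to Spiriva Respimat defined in the package insert for Spiriva Respimat".

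**Who is analysed.** Under Protocol 9.7, "any patient who meets one of the following criteria is treated as ineligible for all analyses"; the criteria are no documented safety observation, registration procedure not followed, and no valid site contract. Protocol 9.7.1 and 9.7.2 otherwise analyse every registered and treated patient.

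SAP 6.3 defines the safety set: "This patient set includes all patients who were documented to have taken at least one dose of Spiriva Respimat", less those with no observation after entry, an invalid registration or no appropriate contract. The efficacy set is the part of the safety set with a baseline and at least one on-treatment value of an effectiveness measure.

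SAP Table 6.2:1 has a category for entrance criteria not met. It holds two codes, A1.1 (Spiriva Respimat before registration) and A1.2 (enrolled before), both excluded from the safety set.

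**What is recorded.** SAP 5.4 lists "Asthma Severity: Severe persistent, Moderate persistent, Mild persistent, Intermittent, Unknown". It also has an indication variable with a level for anything other than bronchial asthma, and a yes/no contraindication variable.

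**Registration.** Protocol 9.2.2.2 says "The necessary variable for registration is gender, date of birth, start date of administration and the reason for use", and adds that ICS treatment is checked in the EDC. Protocol 9.3 includes asthma severity in the registration data.

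**The concern.** The plan does exclude on eligibility, but only on two criteria, and severity, which defines the study population, is not one of them. A correctly registered patient with moderate, mild, intermittent or unknown severity, another indication or a contraindication stays in the safety set and, given baseline and on-treatment data, in the efficacy set.

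According to Protocol 7, the regulator found the 5-µg form suitable only for severe persistent asthma and required this surveillance in those patients as a condition of approval. The report will present its main ADR percentage and its asthma-control result as findings about them. If the sets are mixed, the text of the report and the denominator of its tables describe different groups.

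**Working it through.** **1. Each criterion against the visible rules**

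| Criterion (Protocol 9.2.2.1) | Recorded in | Rule removing a patient who fails it |
|---|---|---|
| First use of Spiriva Respimat | previous medication | SAP A1.1 |
| Not enrolled before | registration | SAP A1.2 |
| Severe persistent asthma | SAP 5.4, five levels | none visible |
| Bronchial asthma as indication | SAP 5.4, two levels | none visible |
| Age 15 or over | date of birth | none visible |
| Background ICS | EDC check, therapies | none explicit; possibly E1 |
| No contraindication | SAP 5.4, yes/no | none visible |

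**2. Could the invalid-registration exclusion cover these patients?** SAP 6.3 removes invalid registrations. Table 6.2:1 gives category E one code, E1, which concerns the registration procedure and points to Protocol 9.2.2.2. That section does not list severity among the necessary variables, whereas 9.3 does. A patient with moderate asthma who is entered in the prescribed way does not trigger E1. For ICS the position is less clear: the check is part of 9.2.2.2, but the text does not say whether a failed check blocks registration or triggers E1.

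**3. Planned size.** Protocol 9.5: 360 − 60 = 300, the safety set given in Protocol 4. Inflating back, 300 / (1 − 60/360) = 360. The figure reproduces and is not in dispute.

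**4. Possible shift in an ADR rate.** The documents give no off-criteria share *f* and no relative risk *k* for such patients; both are assumptions. Take *p* = 1.8% in eligible patients, the rate Protocol 9.5 quotes for several ADRs in Japanese patients with asthma. Pooled rate = (1 − *f*)*p* + *f k p*.

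| *f* | eligible of 300 | *k* = 0.5 | *k* = 2 |
|---|---|---|---|
| 5% | 285 | 1.755% | 1.89% |
| 10% | 270 | 1.71% | 1.98% |
| 20% | 240 | 1.62% | 2.16% |

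The largest shift is 2.16 − 1.80 = 0.36 points. For comparison, 5 cases in 300 have an exact 95% interval of 0.54% to 3.85%.

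For the proportion with any ADR, assume 8% in eligible and 4% in off-criteria patients: (1 − *f*) × 8% + *f* × 4% gives 7.8%, 7.6% and 7.2%. The shifts of 0.2 to 0.8 points compare with a 95% half-width of 1.96 × √(0.08 × 0.92 / 300) = 3.1 points.

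**5. Control status.** SAP Table 7.5:1 scores well controlled at both times as Improvement. Unchanged insufficient control and unchanged poor control are both Worse. Among patients whose status does not change, the improved share therefore equals the share who were well controlled at baseline. If off-criteria patients start better controlled (an assumption), their inclusion raises the improved share even with no change in anyone.

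As an illustration with assumed rates of 45% improved in eligible and 70% in off-criteria patients: (1 − *f*) × 45% + *f* × 70% gives 46.3%, 47.5% and 50.0%. The shifts of 1.3 to 5.0 points compare with a half-width of 1.96 × √(0.45 × 0.55 / 300) = 5.6 points at *n* = 300.

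**6. Cost of an eligible-only ADR column.** Chance of at least one case = 1 − (1 − *p*)^*n*.

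| *n* | *p* = 1.8% | *p* = 1.2% |
|---|---|---|
| 300 | 99.6% | 97.3% |
| 285 | 99.4% | 96.8% |
| 270 | 99.3% | 96.2% |
| 240 | 98.7% | 94.5% |

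Little ability to see these ADRs is lost.

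**The case against.** **The split may already exist.** SAP 6.4, which defines the subgroups, is withheld. SAP 7.8.1 stratifies ADR tables by those subgroups, and Protocol 9.7.2 promises tables by important baseline characteristics. A reader might infer that the plan never separates off-criteria patients; the documents do not support that, because severity may be a 6.4 subgroup. What stands is that a subgroup table changes neither analysis set, nor the overall ADR percentage or the efficacy result computed on them.

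**The sets are not open to everyone.** A reader might also infer that the results describe whoever was registered. They do not: prior users, repeat enrolees, untreated patients, and those without a visit, CRF, safety observation, valid registration or contract are removed.

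**The category lists may be only code lists.** SAP 7 says all possible categories are tabulated, so a level for intermittent asthma does not show that such patients are expected. This is fair, and it means they would be visible in the baseline tables and listings. Visibility does not settle which set they belong to.

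**Severity may be well recorded.** Protocol 9.3 puts it in the registration data and Annex 3 marks it unconditionally at baseline; only one combined bullet in 9.3 says if available. This weakens any claim that severity would be missing, but recording it without a rule does not keep the sets within the objective.

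**Milder patients and room to worsen.** It is tempting to say milder patients have less room to worsen. On the three-level scale of Table 7.5:1 the reverse holds: a well-controlled patient can fall two levels and a poorly controlled one none. The scoring of unchanged status is the sound argument.

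**Size and design.** The study is descriptive, the 9.7 exclusions follow local regulation, and including every treated patient for safety is openly stated. The illustrative shifts lie within sampling error. All of this stands, and it is why these patients should remain in the safety set.

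**Report planning meetings.** SAP 6.2 lets these meetings decide before database lock which observed violations are important. With the SAP dated 1 October 2017 and data collection planned to end on 31 August 2017, such decisions would be made after collection, so they do not replace a written rule.

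**Conclusion.** The point holds for severity, indication, age and contraindication, and in a weaker form for ICS. The visible rules, followed exactly, allow an efficacy result and an overall ADR frequency for a population broader than the one in the objective.

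A large bias is not shown. The off-criteria share, relative ADR risk and improvement rates used above are all assumptions, and the share could be close to zero. Under them a 1.8% ADR moves by at most 0.36 points and the improved share by at most 5.0 points. The case rests on attribution: figures reported for severe persistent asthma should come from patients with severe persistent asthma. The conclusion is limited to the visible text; if SAP 6.4 already gives ADR results for eligible patients, that part of the gap closes and the efficacy set remains to be fixed.

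**What to change.** - Add category-A codes to SAP Table 6.2:1 for: indication not bronchial asthma; severity not severe persistent, or unknown; age under 15; no ICS at start; contraindication present. Mark them as excluded from the efficacy set only, and say so in SAP 6.3.
- Keep these patients in the safety set. Report the primary ADR frequency in three columns: patients meeting all criteria, patients who do not, and the total. If 6.4 already does this, refer to it in SAP 7.8.1.
- State what a failed ICS check in the EDC triggers, and whether it falls under E1.
- Make the registration variables in Protocol 9.2.2.2 agree with 9.3 on severity, and reconcile the conditional collection of severity in 9.3 with the unconditional mark in Annex 3.

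**Cost.** SAP wording and extra columns in the ADR table; the plan already provides for recording the variables. The efficacy set becomes somewhat smaller: at assumed shares of 5%, 10% or 20% of 300, by at most 15, 30 or 60 patients.

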9.7.1 Analyses of outcome events

The analysis of outcome events will include all patients registered in the study and receiving the Spiriva Respimat treatment. All outcome events are based on reported AE data which will be handled according to BI standards.

9.7.2 Safety analyses

The safety analysis will include all patients registered in the study and receiving the Spiriva Respimat treatment. In general, safety analyses will be descriptive in nature, will be based on BI standards, and will focus on ADRs related to the Spiriva Respimat treatment.

AEs will be coded using the current version of the Medical Dictionary for Regulatory Activities (MedDRA) and will be based on the concept of treatment emergent AEs. To this end, all AEs occurring between the first intake of Spiriva Respimat prescribed at baseline visit and within 30 days (inclusive) after the last intake will be considered 'treatment emergent'. An AE is considered to be ADR if either the physician who has reported the AE or the sponsor assesses its causal relationship as 'related'.

The frequency of AEs/ADRs will be tabulated by system organ class and preferred term for overall and for subgroups based on the important baseline characteristics.

No imputation is planned for missing AE data except for missing onset dates which will be handled according to BI standard.

9.7.3 Analyses of other variables

Descriptive statistics will be calculated for all outcomes.

A missing score for an item may be replaced as the mean score of the available data. In case of a missing ACQ 6 score, the missing score will not be imputed.

For other variables, missing data will not be imputed.

9.7.4 Interim analyses

Several interim analyses will be performed for the purpose of creating periodic safety update reports to the local authority (every 6 to 12 months depending on the time from the approval).

9.8 QUALITY CONTROL

All processes are conducted according to GPSP SOPs and GPSP working instruction. Appropriate records and documents are stored based on the GPSP SOPs and these processes are checked by internal self-check.

9.9 LIMITATIONS OF THE RESEARCH METHODS

No randomized assignment of patients to the survey is implicated. This may induce selection bias. The site will be nominated by the availability of conducting the study with a peak flow meter, and might have a more intensive observation compared with the non-selected site.

9.10 OTHER ASPECTS

9.10.1 INFORMED CONSENT, DATA PROTECTION, STUDY RECORDS

Standard medical care (prophylactic, diagnostic and therapeutic procedures) remains the responsibility of the patient's treating physician.

The rights of the investigator and of the sponsor with regard to publication of the results of this PMS are described in the contract.

9.10.1.1 STUDY APPROVAL, PATIENT INFORMATION, AND INFORMED CONSENT

The review by IRB is not mandatory for conducting PMS in Japanese GPSP. The sponsor will enter into a contract with a representative (e.g., head of hospital) in accordance with GPSP. Written informed consent prior to patient participation in the trial is not a regulatory or legal requirement in accordance with GPSP.

9.10.1.2 DATA QUALITY ASSURANCE

This PMS is to be conducted in accordance with both the in-house PMS SOP and working instructions which are in compliance with GPSP. This study should be conducted in compliance with SOP 001-MCS-90-118.

9.10.1.3 RECORDS

Case Report Forms (CRFs) for individual patients will be provided by the sponsor via the Electronic Data Capture (EDC) system.

9.10.1.3.1 Source documents

Source documents provide evidence for the existence of the patient and substantiate the integrity of the data collected. Source documents are filed at the investigator's site.

Data entered in the eCRFs that are transcribed from source documents must be consistent with the source documents or the discrepancies must be explained. The investigator may need to request previous medical records or transfer records, depending on the study; also current medical records must be available.

For eCRFs, all data must be derived from source documents.

9.10.1.3.2 Direct access to source data and documents

Direct access to source data and documents for PMS is not allowed in Japan.

9.10.1.4 STATEMENT OF CONFIDENTIALITY

Individual patient medical information obtained as a result of this PMS is considered confidential and disclosure to third parties is prohibited with the exceptions noted below. Patient confidentiality will be ensured by using patient identification code numbers.

Data generated as a result of the PMS needs to be available for inspection on request by the regulatory authorities.

10. PROTECTION OF HUMAN SUBJECTS

There is no regulation or requirement for ensuring the well-being and rights of participants in a non-interventional observational study.

11. MANAGEMENT AND REPORTING OF ADVERSE EVENTS/ADVERSE REACTIONS

11.1 DEFINITIONS OF ADVERSE EVENTS

Adverse event

An adverse event (AE) is defined as any untoward medical occurrence, including an exacerbation of a pre-existing condition, in a patient in a study who received a pharmaceutical product. The event does not necessarily have to have a causal relationship with this treatment. An AE can therefore be any unfavourable and unintended sign (including an abnormal laboratory finding), symptom, or disease temporally associated with the use of a medicinal product, whether or not considered related to the medicinal product.

Adverse Drug Reaction (ADR)

A response to a medicinal product which is noxious and unintended.

Response in this context means that a causal relationship between a medicinal product and an adverse event is at least a reasonable possibility.

Adverse reactions may arise from use of the product within or outside the terms of the marketing authorisation or from occupational exposure. Conditions of use outside the marketing authorisation include off-label use, overdose, misuse, abuse and medication errors.

Serious adverse event

A serious adverse event - is defined as any AE which

- results in death,
- is immediately life-threatening,
- requires in-patient hospitalization, or
- prolongation of existing hospitalization
- results in persistent or significant disability or incapacity, or
- is a congenital anomaly / birth defect

Life-threatening in this context refers to a reaction in which the patient was at risk of death at the time of the reaction; it does not refer to a reaction that hypothetically might have caused death if more severe.

Medical and scientific judgement should be exercised in deciding whether other situations should be considered serious reactions, such as important medical events that might not be immediately life threatening or result in death or hospitalisation but might jeopardise the patient or might require intervention to prevent one of the other outcomes listed above. Examples of such events are intensive treatment in an emergency room or at home for allergic bronchospasm, blood dyscrasias or convulsions that do not result in hospitalisation or development of dependency or abuse. Any suspected transmission via a medicinal product of an infectious agent is also considered a serious adverse reaction.

Every new occurrence of cancer will be considered as SAE regardless of the duration between discontinuation of the study medication and the occurrence of the cancer.

Adverse Event of Special Interest (AESI)

The term AESI relates to any specific AE that has been identified at the project level as being of particular concern for prospective safety monitoring and safety assessment within this study, e.g. the potential for AEs based on knowledge from other compounds in the same class.

No AESIs have been defined for this study.

